5.3. Analysis Populations

5.3.1. Full Analysis Set Population

The FAS population includes all subjects enrolled in the study who received at least 1 dose of INCAGN01949. The FAS population will be used for the summary of demographics, baseline characteristics, subject disposition, safety, study drug administration, and analyses of all efficacy data.

5.3.2. Part 1 Full Analysis Set Population

The Part 1 FAS population includes all subjects in the FAS population enrolled in Part 1 of the study who received at least 1 dose of INCAGN01949.

5.3.3. Part 2 Full Analysis Set Population

The Part 2 FAS population includes all subjects in the FAS population enrolled in Part 2 of the study who received at least 1 dose of the MTD/PAD of INCAGN01949. Subjects tested in Part 1 (dose escalation and safety expansion) who are treated at the MTD/PAD and in Part 2, are of the same tumor type, and who meet inclusion/exclusion criteria used for the tumor type of interest in Part 2 will be combined for both safety and efficacy summary purposes.

Specific analysis populations to be used for evaluating the Simon 2-stage efficacy rules include the following subgroups:

- Part 2 FAS population subjects with adenocarcinoma of endometrium
- Part 2 FAS population subjects with melanoma
- Part 2 FAS population subjects with ovarian cancer
- Part 2 FAS population subjects with NSCLC
- Part 2 FAS population subjects with RCC

Table summaries, unless otherwise indicated, will be provided by tumor-specific cohort.

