4.1.1.2. Safety Expansion

In order to evaluate additional [REDACTED] activity of INCAGN01949 and confirm the preliminary safety of the dose-escalation cohorts, Part 1 of the study may include safety expansion cohorts evaluating doses and schedules equivalent to or lower than the highest dose levels determined to be safe and/or doses determined to be pharmacologically active. The alternative dose administration schedules and fixed doses (equivalent to or less than the MTD determined during dose escalation) that may be explored during the safety expansion would depend on PK, [REDACTED] and safety results.

A maximum of 36 subjects will be enrolled into the Part 1 safety expansion, and each Part 1 safety expansion cohort will enroll up to 9 evaluable subjects. If < 3 of 9 evaluable subjects have a DLT, then the cohort will be deemed safe. If > 1 safety expansion cohort is deemed safe, then a recommended dose and schedule will be determined in conjunction with the investigators and sponsor based on all available safety, PK, [REDACTED] results. The safety expansion cohorts may be run in parallel to Part 2 and may be limited by the sponsor to subjects with specific tumor types to achieve a balance across cohorts.

4.1.2. Part 2

[figure not shown]
Part 2 of the study will further evaluate the safety, tolerability, preliminary efficacy, PK, and pharmacologic activity of the recommended dose of INCAGN01949 in subjects with advanced or metastatic adenocarcinoma of the endometrium, ovarian cancer, RCC, melanoma, and NSCLC (squamous and nonsquamous). Each cohort will consist of an individual tumor type. A Simon 2-stage design will be used with a stopping rule to allow for early termination of a particular cohort at the end of Stage 1 if there are insufficient responses observed. During Stage 1, 9 subjects will be enrolled into each cohort; if no responses are observed within a cohort, then the cohort will be discontinued. If at least 1 response is observed, then 8 additional subjects will be enrolled into that cohort (Stage 2), for a maximum of 17 subjects per cohort.

Subjects will continue to receive INCAGN01949 until Protocol-defined withdrawal criteria are met. Continuous evaluation of toxicity events will be performed throughout enrollment in Part 2

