3.1. Dose Escalation and Expansion

3.1.1. Part 1 – Dose Escalation

The PAD is defined as a dose that provides a maximal biochemical effect, or an increase in biomarkers of immune activity.

A DLT will be defined as the occurrence of a toxicity, with the exception of events clearly associated with the underlying disease, disease progression, a concomitant medication, or comorbidity; the list of toxicities that will be designated as dose limiting toxicities are provided in Table 3 of the Protocol.

In Part 1 of the study, the MTD will be defined as 1 dose level below that at which \geq one-third of subjects in a particular cohort have DLTs.

In Part 1, subjects with advanced or metastatic solid tumors who progressed after treatment with available therapies that are known to confer clinical benefit, who are intolerant to treatment, or refuse standard treatment will be enrolled.

In the dose-escalation part of the study, a 3 + 3 design will be used to determine the MTD or PAD of INCAGN01949. A minimum of 3 evaluable subjects will be enrolled in each cohort beginning with Cohort 1 (7 mg; starting dose). There will be a waiting period of 48 hours between dose administration of the first subject and second subject of each dose cohort. The first 3 subjects enrolled within a cohort will be observed for a DLT observation period of 28 days

before the next cohort begins enrollment. The dose will be escalated if 0 of the first 3 evaluable subjects enrolled has a DLT. If 1 of the first 3 evaluable subjects enrolled has a DLT, then the cohort will be expanded to include 3 additional evaluable subjects, and if no DLT occurs in the additional 3 subjects, then the dose will be escalated. If a DLT occurs in one-third or more of the expanded cohort, then the MTD will be deemed to be exceeded, and the prior dose level will be considered the MTD. If only 3 subjects were treated at the MTD or PAD, then a minimum of 3 additional subjects will be enrolled before this dose is administered in Part 2 of the study.

If Cohort 1 (7 mg; starting dose) exceeds the MTD, the sponsor and investigators will consider dosing INCAGN01949 at 2 mg (Cohort -1), and/or investigate 7 mg at alternate dose schedules (eg, every 3-week administration), based on available safety, PK, [REDACTED] [REDACTED] data. If an alternate schedule is tested and determined to be safe, re-escalation of INCAGN01949 will proceed according to [Table 1](#).

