Throughout the treatment period, if > 33% of subjects (a minimum of 6 subjects) experience a \geq Grade 3 toxicity related to study drug after completing \geq 4 cycles, then dose administration will be stopped, and the MNTD will be determined in conjunction with the investigators and sponsor based on all available safety data.

Additional subjects will be enrolled in a cohort to achieve the minimum of 3 evaluable subjects. Subjects who drop out for reasons other than a DLT (eg, events clearly associated with the underlying disease, disease progression, concomitant medication, or comorbidity) during the 28-day DLT observation period will be considered nonevaluable and will be replaced. Dose modifications should not be made during the DLT observation period without discussion with the medical monitor. Intrasubject dose escalation is not permitted; however, once the recommended dose and schedule have been determined, ongoing subjects in Part 1 may be permitted to escalate the dose to the recommended level with approval of the medical monitor. The cohorts and dose levels are shown in [Table 1](#).

Table 1: INCAGN01949 Dose Levels and Cohort

Cohort	Dose of INCAGN01949 ^a
-1	2 mg ^b
1 (starting dose)	7 mg
2	20 mg
3	70 mg
4	200 mg
5	350 mg
6	700 mg

^a Additional dose schedules may be explored that would depend on PK, [REDACTED], and safety results.

^b Subjects who require a dose reduction below 2 mg should be discontinued from study drug.

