3.1.2. Part 1 – Safety Expansion

In order to evaluate additional [REDACTED] activity of INCAGN01949 and confirm the preliminary safety of the dose escalation cohorts, Part 1 of the study may include safety expansion cohorts evaluating doses and schedules equivalent to or lower than the highest dose

levels determined to be safe and/or doses determined to be pharmacologically active. The alternative dose administration schedules and fixed doses (equivalent to or less than the MTD determined during dose escalation) that may be explored during the safety expansion would depend on PK, [REDACTED], and safety results.

A maximum of 36 subjects will be enrolled into the Part 1 safety expansion, and each Part 1 safety expansion cohort will enroll up to 9 evaluable subjects. If < 3 of 9 evaluable subjects have a DLT, then the cohort will be deemed safe. If > 1 safety expansion cohort is deemed safe, then a recommended dose and schedule will be determined in conjunction with the investigators and sponsor based on all available safety, PK, [REDACTED] results. The safety expansion cohorts may be run in parallel to Part 2 and may be limited by the sponsor to subjects with specific tumor types to achieve a balance across cohorts.

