5.2. Treatment Groups

This is a Phase 1/2, open-label, nonrandomized, multicenter, dose-escalation study. Up to 7 doses will be tested. Data will be summarized overall and by treatment group. Treatment group is defined as the dose regimen initially assigned. Treatment cycles will begin every 14 days (\pm 3 days) but are flexible for different dose schedules based on emerging safety, PK, [REDACTED] data.

- 2 mg
- 7 mg
- 20 mg
- 70 mg
- 200 mg
- 350 mg
- 700 mg

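### SAP 5.3.3 combines Part 1 subjects treated at the MTD/PAD with Part 2 subjects without requiring that they started on the Part 2 dose and schedule

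*SAP*

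**What the plan says.** SAP 5.3.3 first defines the Part 2 full analysis set as subjects enrolled in Part 2 "who received at least 1 dose of the MTD/PAD of INCAGN01949". It then turns to Part 1 subjects, from dose escalation and safety expansion, "who are treated at the MTD/PAD and in Part 2, are of the same tumor type" and who satisfy the Part 2 eligibility criteria for that tumor type. These "will be combined for both safety and efficacy summary purposes". The section says nothing about starting dose or schedule.

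Other sections bear on this:

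- SAP 5.2: "Treatment group is defined as the dose regimen initially assigned".
- SAP 3.1.1: once the recommended dose and schedule are known, "ongoing subjects in Part 1 may be permitted to escalate the dose to the recommended level with approval of the medical monitor". Protocol 4.1.1.1 and 5.4.1 allow the same.
- SAP 3.1.1: if only 3 subjects were treated at the MTD or PAD, "a minimum of 3 additional subjects will be enrolled before this dose is administered in Part 2 of the study". The MTD or PAD is thus expected to be the dose carried into Part 2.
- Protocol 4.1.1.2: Part 1 may include safety expansion cohorts "evaluating doses and schedules equivalent to or lower than the highest dose levels determined to be safe". SAP 3.1.2 adds that if more than one such cohort is deemed safe, "a recommended dose and schedule will be determined in conjunction with the investigators and sponsor".
- Protocol 5.2.1 and SAP 3: Part 2 subjects receive one recommended dose and schedule.

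**The concern.** The combined summaries are meant to describe the Part 2 regimen in a given tumor type. The pooling rule selects on having been treated at a dose, which a subject can satisfy late in treatment or on another schedule. A subject who qualifies that way brings in everything recorded since Day 1, including responses, adverse events and progression-free time from before the escalation.

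Escalated subjects are also a selected group: they must still have been on study drug when the recommended dose was chosen. Early progressors on the lower dose cannot join them, so their PFS contains time in which no event could have occurred. The bias in PFS therefore tends to be favorable, while the bias in response rate and AE rates can go either way.

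**Working it through.** **1. The plan's own figures.** For the design with 9 then 8 subjects, stopping at 0/9 and requiring at least 3/17, the chance of a positive result at response rate p is the sum over x = 1 to 9 of P(X1 = x) × P(X2 ≥ 3 − x), with X1 ~ Bin(9, p) and X2 ~ Bin(8, p). This gives 0.0466 at p = 5% and 0.812 at p = 25%, consistent with the stated 1-sided 0.05 and 80%. Stage 1 termination at 25% is 0.75^9 = 7.5%, as in SAP Table 8. The design arithmetic is sound and this point does not touch it.

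**2. Who fits the pooling rule.** Take Part 1 subjects of a matching tumor type who meet the eligibility criteria.

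| Part 1 history | Started on the Part 2 regimen? | Pooled under 5.3.3? |
|---|---|---|
| Recommended dose and schedule from Day 1 | Yes | Yes |
| Lower dose, later escalated to the recommended level | No | Yes on a literal reading; no if SAP 5.2 governs |
| Recommended dose on another schedule | No | Yes on a literal reading; SAP 5.2 speaks of a regimen but lists doses only |
| Lower dose throughout | No | No |

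The two middle rows are the problem. The SAP can separate schedules when it means to: 8.2.2 does so for DLTs and 8.2.4 for immune-related AEs. Section 5.3.3 does not.

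**3. Which data they bring.** An objective responder needs CR or PR at any postbaseline visit before first PD (SAP 7.4.2). PFS runs from Day 1 (SAP 7.4.8), which is the first dose of study drug (SAP 4.1.1). Treatment-emergent AEs count after the first dose (SAP 8.2.1). None of these restarts at escalation.

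**4. Size, by illustration.** The documents give no number of escalated or pooled subjects and no response rate by regimen. Assume 17 Part 2 subjects at the 25% target rate and m pooled subjects with response rate q. The expected pooled rate is (17 × 0.25 + m × q)/(17 + m).

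| m | q = 5% | q = 15% | q = 25% |
|---|---|---|---|
| 1 | 4.30/18 = 23.9% | 4.40/18 = 24.4% | 25% |
| 2 | 4.35/19 = 22.9% | 4.55/19 = 23.9% | 25% |
| 3 | 4.40/20 = 22.0% | 4.70/20 = 23.5% | 25% |
| 9 | 4.70/26 = 18.1% | 5.60/26 = 21.5% | 25% |

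The row m = 9 is an outer case: a full safety expansion cohort, all of one tumor type, on a different schedule.

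In observed counts, 3/17 = 17.6% becomes 3/18 = 16.7%, 3/19 = 15.8% or 3/20 = 15.0% with 1, 2 or 3 pooled nonresponders. It becomes 4/18 = 22.2% with one pooled subject whose response came on the earlier dose. For scale, the plain exact 95% interval for 3/17 is 3.8% to 43.4% (the SAP plans a two-stage method instead).

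**The case against.** The best defense is SAP 5.2. It sits in the general methodology and attributes subjects to the regimen initially assigned, and no other SAP rule attributes them by a later dose. On that view, treated at the MTD/PAD simply means assigned to that cohort. This is a reasonable guess at the intent, but 5.2 defines treatment groups, 5.3.3 neither cites nor uses it, and Part 2 tables are by tumor cohort. The preceding sentence of 5.3.3 uses an as-received test, at least one dose of the MTD/PAD, which favors the literal reading.

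A second defense is eligibility. Exclusion 15 bars prior OX40 agonist treatment and exclusion 3 sets washouts of up to 28 days for antibodies and immunotherapy, so a subject escalating from a lower dose of this drug would fail both if tested at escalation. But eligibility is normally judged at study entry, and nothing in 5.3.3 moves it.

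Three further objections stand and limit the point:

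- A recommended dose that differs from the MTD/PAD is largely a matter of terminology. SAP 3.4.2 and SAP 9 describe the same Stage 1 subjects once by the MTD or PAD and once by the recommended dose, and SAP 3.4.1 lets the PAD stand in for the MTD. Only the schedule part remains.
- A reader might infer that any mixture would be hidden, because the Part 2 efficacy shells are headed Recommended Dose and the AE shells show only cancer type. For dose that is not so: the Part 2 exposure tables (3.1.1.2 and 3.1.2.2) show dose in mg, the latter by cycle with minimum and maximum, and Listing 2.6.1 covers dosing. Schedule would be harder to see.
- It is not clear that pooled subjects enter the tables labelled Part 2 FAS, since that set is limited to subjects enrolled in Part 2. The SAP does not say where the combined summaries appear.

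**Conclusion.** The pooling rule is looser than its purpose requires, and the gap is real on the text. Mixing occurs only if a matching, eligible Part 1 subject escalated to the recommended level or received that dose on another schedule. With 1 to 3 such subjects, the expected response rate shifts by 1.1 to 3.0 points under the assumed 25% versus 5% contrast, which is the design alternative against the design null and therefore wide. This is small beside the sampling uncertainty in 17 subjects, and SAP 3.3 calls all analyses exploratory. If nobody is pooled, or all pooled subjects started on the Part 2 regimen, the effect is zero.

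A reader might infer that pooled subjects could also tip the Simon go/no-go rule, because the Simon populations are listed directly below the pooling sentence. The documents do not support that. The combination is for summary purposes only, Stage 1 uses the first 9 evaluable subjects enrolled at the recommended dose and schedule (SAP 3.4.2 and 9), and the final rule counts the first 17 (Protocol 9.4.1.1). Nor does the MTD/PAD wording in the Part 2 FAS definition itself cause mixing, since everyone enrolled in Part 2 receives the recommended regimen.

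Severity: minor.

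**What to change.** In SAP 5.3.3, replace the condition of being treated at the MTD/PAD by this: a Part 1 subject is combined with a Part 2 cohort only if the initially assigned dose and schedule equal the recommended dose and schedule evaluated in Part 2. This applies the principle of SAP 5.2 and extends it explicitly to schedule. Show Part 1 subjects who escalated to the recommended level in a separate listing. As a clarification only, add that pooled Part 1 subjects are not counted in the Simon rules.

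The cost is SAP wording and possibly a few fewer pooled subjects in the combined summaries. No change to the protocol, data collection or sample size is needed.

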5.3.4. Per Protocol Population

Subjects in the FAS population who are considered to be sufficiently compliant with the Protocol comprise the PP population.

[figure not shown]
The following procedures will be performed to identify those subjects who are to be excluded from the PP population before the database lock:

- Clinical review of Protocol deviations/violations
- Clinical review of concomitant medications (prohibited medications) as defined in Section 5.6.3 of the Protocol.
- Clinical review of the dose administration and drug accountability listing.

5.3.5. Pharmacokinetic [REDACTED] Evaluable Populations

5.3.5.1. Pharmacokinetic Evaluable Population

The PK evaluable population will include all subjects who received at least 1 dose of INCAGN01949 and provided at least 1 postdose sample (1 PK measurement). The study pharmacokineticist will review data listings of study drug administration and sample records to identify subjects to be excluded from analyses of PK data.

6. BASELINE, EXPOSURE, AND DISPOSITION VARIABLES AND ANALYSES

[Appendix A](#) provides a list of data displays and sample data displays.

6.1. Baseline and Demographics, Physical Characteristics, and Disease History

6.1.1. Demographics

The following demographics will be summarized for the Part 1 FAS population by dose level and for the Part 2 FAS population by tumor type: age, sex, race, ethnicity, and ECOG performance status.

6.1.2. Baseline Disease Characteristics and Disease History

For each type of tumor, primary tumor histology, date of initial diagnosis, stage at initial diagnosis, current stage of disease, current site of disease, and tumor markers will be summarized for all subjects in the Part 1 FAS population by dose level and Part 2 FAS population by tumor type.

6.1.3. Prior Therapy

Number of prior systemic cancer therapy regimens and prior immunotherapy will be summarized for all subjects in the FAS population by dose level in Part 1 and by tumor type in Part 2. Regimen name, component drugs, start and stop date, purpose of the regimen, best response, reason for discontinuation, and date of relapse/progression will be listed by total number and by number of prior systematic cancer therapies taken for both advanced and metastatic disease.

Number of subjects who received prior radiation will be summarized for the FAS population. Radiotherapy type, body site, start and stop date, total dose, and best response will be listed.

Number of subjects who had prior surgery or surgical procedure for the malignancies under study will be summarized for the FAS population. Date and description of the surgery/procedure will be listed.

Number of subjects with prior immunotherapy and prior anti-PD-1/PD-L1 therapy will be summarized for the Part 1 FAS population by dose level and the Part 2 FAS population by tumor type. Prior immunotherapy type, start and stop date, total dose, and best response will be listed.

6.1.4. Medical History

For subjects in the Part 1 FAS population by dose level and Part 2 FAS population by tumor type, medical history will be summarized by assigned treatment group. This summation will include the number and percentage of subjects with significant medical history for each body system/organ class as documented on the CRF.

6.2. Disposition of Subjects

The number and percentage of subjects who were enrolled, treated, completed the study, discontinued study treatment with a primary reason for discontinuation, and discontinued from the study with a primary reason for withdrawal will be summarized for the subjects in the Part 1 FAS population by dose level and Part 2 FAS population by tumor type. The number of subjects enrolled by site will also be provided by treatment group.

6.3. Protocol Deviations and Violations

Protocol deviations and violations recorded on the CRF will be presented in the subject data listings.

6.4. Exposure

For subjects in the FAS population, exposure to INCAGN01949 will be summarized descriptively as the following:

- **Total number of infusions:** Total number of infusions per subject by the time of date cutoff will be the total number of infusions per subject with a nonzero dose of INCAGN01949.
- **Dose administered per cycle:** The actual dose administered (in mg) per cycle.
- **Total dose administered in mg/kg:** The total actual dose administered (in mg/kg) across cycles for each subject will be determined according to the following calculation:

For an infusion i , let C_i be the concentration (in mg/mL) of INCAGN01949 and V_i be the total volume administered (in mL) reported on the INCAGN01949 dosing CRF; let W be the subject's baseline weight (in kg), and N be the total number of infusions

$$\text{Total dose administered (in mg/kg)} = \sum_{i=1}^N \frac{C_i \times V_i}{W}.$$

- **Average dose in mg/kg:** The average dose (in mg/kg) will be the total dose administered (in mg/kg) divided by the total number of infusions.
- **Total dose administered in mg:** Total actual dose administered (in mg) across cycles for each subject will be determined according to the following calculation:
For an infusion i , let C_i , V_i , and N be defined as above
Total dose administered (in mg) = $\sum_{i=1}^N C_i \times V_i$.
- **Average dose in mg:** The average dose (in mg) will be the total dose administered (in mg) divided by the total number of infusions.

6.5. Prior and Concomitant Medication

Prior medications and concomitant medications will be coded using the WHO Drug Dictionary and summarized by WHO drug class and WHO drug term by dose level in the Part 1 FAS population and by tumor type in the Part 2 FAS population. Results will be summarized as number and percentage of subjects with prior and concomitant medications by PT and WHO drug class.

